#### 5.9.3 Dose Uniformity

Photon Therapy Goals: At least 95% of the protocol-specified dose should encompass 100% of the PTV and no more than 10% of PTV should receive greater than 110% of the protocol dose as evaluated by DVH. The 100% isodose should be equal to the protocol specified dose. All methods of generating more uniform dose distributions are encouraged. For craniospinal treatments, the dose will be measured at the midplane of the cranial volume and at the posterior border of the vertebral body the spinal field(s) including the dose at the central ray. Effort should be made to minimize inhomogeneity at the craniocervical junction when possible and the gradient of dose across the spinal cord.

IRB Approval date:

Rev. 3.2 dated: 1/19/2023 Protocol document date: 1/19/2023 St. Jude Children's Research Hospital

IRB NUMBER: Pro00004349

Proton Therapy Goals: At least 95% of the protocol-specified dose should encompass 100% of the CTV and no more than 10% of CTV should receive greater than 110% of the protocol dose as evaluated by DVH. The 100% isodose should be equal to the protocol specified dose. The PTV may be used to select the appropriate beam size and beam arrangements to achieve lateral coverage of the targeted volume and to minimize heterogeneity. The lateral margin for proton therapy should be approximately 3mm. The PTV will not be used to determine the distal range for the individual proton beams. The proton distal target margin will be determined per beam based on the distal aspect of the CTV and additional margin(s) meant to account for range uncertainty and the SM and IM components of the PTV which are understood for this group of patients and which may affect the proton distal range.‡

Proton Distal Target Margin† = CTV + Range Uncertainty + Set-up Margin + Internal Margin

- CTV = the distal aspect of the CTV
- Range Uncertainty = 3% of the water-equivalent range of the CTV at max depth
  - $\circ$  > 1mm
- Set-up Margin = set-up, mechanical, dosimetric and registration uncertainties
  - Protons are relatively unaffected by set-up uncertainty in axis of beam. Setup errors for brain in general do not have an impact on range per se.
  - Uncertainty in hardware and software no assigned value available
     Uncertainty in accuracy of image registration
    - > 1mm
- Internal margin = compensates for all variations in site, size and shape of the tissues contained in or adjacent to the CTV. We assume no internal organ motion.
  - $\circ$  > 1mm

†The proton distal range may be adjusted at the discretion of the treating radiation oncologist based on normal tissue dose concerns.

‡The uncertainty of distal margin has been estimated to be as large as 3-4mm.

For the rare case treated using photon therapy due to equipment failure, at least 95% of the protocol-specified dose should encompass 100% of the PTV and no more than 10% of PTV should receive greater than 110% of the protocol dose as evaluated by DVH. The 100% isodose should be equal to the protocol specified dose. Methods of generating more uniform dose distributions are encouraged.

When pencil beam scanning techniques are used with scenario-based optimization (e.g., robust optimization), the plan may be optimized for 100% of the CTV to receive 95% of the protocol-specified dose. The protocol-defined PTV may be reviewed to confirm coverage.

#### 5.9.4 Tissue Heterogeneity

Calculations must take into account tissue heterogeneity and should be performed with CT-based treatment planning to generate dose distributions and treatment calculations from CT densities.

#### 5.9.5 Interruptions, Delays and Dose Modifications

There will be no planned rests or breaks from treatment, and once radiation therapy has been initiated, treatment will not be interrupted except for any life threatening infection or severe hematological toxicity defined as ANC < 300/µL or platelets less than 20,000/µL during the course of treatment. Blood product support is not required. The reason for any interruptions greater than 3 treatment days should be recorded in the patient treatment chart. There should be no modifications in dose fractionation due to age or field size.

Sequencing Contingencies: CSI will generally be given first, followed by boost therapy. Boost therapy may be initiated prior to craniospinal irradiation if required by the medical condition. In all cases when CSI is deferred, it should be initiated as soon as medically feasible, before the completion of boost therapy if feasible. If CSI is interrupted for >4 days for medical reasons, the boost should be started until CSI can be resumed.

#### 5.10 **Treatment Technique**

#### 5.10.1 Beam Configuration

Every attempt should be made to minimize dose to organs at risk without compromising coverage of the target volume. Three-dimensional conformal or intensity-modulated radiation therapy using photons or protons are required to minimize dose to normal tissues.

#### 5.10.2 Field Shaping

Photon field shaping will be done with multileaf collimation.

#### 5.10.3 Patient positioning

Reproducible setups are critical and the use of immobilization devices is strongly encouraged. The patient may be treated in any appropriate, stable position. Consideration should be given to implications for inter and intra-fraction motion when using non-standard position approaches.

#### 5.10.4 Immobilization devices

Standard immobilization devices for the torso, extremities or head and neck are to be used. For IMRT delivery approaches, the methods used for localization and immobilization of both patient and tumor are critical. The imaging studies should

> St. Jude Children's Research Hospital IRB Approval date:

IRB NUMBER: Pro00004349 IRB APPROVAL DATE: 02/01/2023

Protocol document date: 1/19/2023

provide a clear assessment of the target volume with the patient in the treatment position.

#### 5.10.5 Special considerations

Anesthesia or sedation may be required in certain patients, such as very young patients, to prevent movement during simulation and daily treatments.

#### 5.10.6 Motion Management and Margins to Account for Target Volume

Considering motion of normal tissues and target volumes is important. The internal target volume (ITV) is defined as the CTV surrounded by the IM component of the PTV and is meant to account for potential motion or changes in the CTV. The planning organ at risk volume (PRV) includes the corresponding organ at risk (OAR) volume surrounded by a margin to compensate for motion or physiologic change in the OAR. If adequate clinical data do not exist to define the IM component of the PTV or the PRV margin, the following suggestions are provided:

- Margin matching the PTV margin may be added to OAR to form the PRV.
- Brain tumors susceptible to cyst expansion should be monitored closely.
- Any change in clinical condition or anatomy related to hydrocephalus, VP shunt placement, subdural fluid, pseudomeningocele or steroid use should be monitored carefully and with repeat imaging when indicated.
- Portal and volumetric imaging may be performed at the completion of individual treatment sessions to assess the individual patient's set-up uncertainty and prescribe the appropriate margins to account for set-up uncertainty.

#### 5.10.7 Radiosurgery

Under certain circumstances patients will be treated with primary radiosurgery. These patients will be treated with tumor ablative doses according to institutional and cooperative group guidelines. Tolerances to normal tissue structure according to the same guidelines will also be observed.

Radiosurgery is a standardized procedure and will be considered for the primary or boost treatment of selected patients with residual primary or metastatic disease. This treatment may be carried out using the linear accelerator or Gamma Knife. Patients will undergo a CT or MR scan for stereotactic localization following the placement of a neurosurgical head frame. A dose in the range of 1000-1500cGy will be delivered to the patients receiving boost treatment and generally 1500-2100cGy to patients receiving primary radiosurgery. The dose selected depends on the size of the target volume. The treatment will be single fraction and the dose will be described to the isodose line encompassing the target volume. In general, the target volume will be encompassed by the 80-90% isodose surface for linac-

> St. Jude Children's Research Hospital IRB Approval date:

IRB NUMBER: Pro00004349

based radiosurgery and the 50-60% isodose surface for Gamma Knife. The brainstem dose will be less than 1200cGy and the dose to the chiasm will be limited to 800cGy.

# **5.11 Treatment Planning Procedures**

Craniospinal Irradiation: Patients may be simulated and treated in the prone or supine position using customized immobilization devices that allow for verification of cranial and spinal field junctions. Treatment will be given using standard techniques, encompassing the entire subarachnoid volume (both brain and spine). The technique should assure coverage at the cribriform plate and temporal fossae intracranially; the full width of the spinal subarachnoid space (dosimetrically to include the medial aspect of the neural foramina) down to the bottom of the thecal space (as indicated by sagittal spinal MR).

Infratentorial Irradiation: Consideration should be given to minimizing dose to the brainstem and spinal cord.

Supratentorial Irradiation: Consideration should be given to minimize dose to the optic apparatus including the eyes, nerves and chiasm.

Metastatic Site Irradiation: MR visible intracranial metastatic disease should be treated concurrently with the primary site and when feasible joined to the primary site volume. The decision to treat separate or combined primary and metastatic boost volumes should be based on limiting normal tissue irradiation. Spinal metastatic disease should be treated concurrently with the primary site treatment.

#### 5.12 Organs at Risk

The organs at risk guidelines in this section are recommendations. If the recommended doses to the organs at risk are exceeded because of target volume coverage requirements or other conditions, an explanation should be included in the quality assurance documentation. Note these guidelines are for the current treatment protocol and do not represent cumulative target doses.

#### 5.12.1 Cochleae

- D50% < 3500cGy Goal (single cochlea)
- D50% < 2000cGy Preferred (single cochlea)
- Comment There is no dose limit for the cochleae.
- Structure definition Each cochlea will be contoured on the treatment planning CT as a circular structure within the petrous portion of the temporal bone. The contour should appear on at least two successive CT images.

IRB Approval date:

#### 5.12.2 Optic Globes

• D50% < 1000cGy and D10% < 3500cGy – Goal

St. Jude Children's Research Hospital

IRB NUMBER: Pro00004349
IRB APPROVAL DATE: 02/01/2023

Protocol document date: 1/19/2023

- D50% < 2000cGy and D10% < 5400cGy Maximum
- Comment Effort should be made to avoid direct treatment of the anterior chamber of the eye and minimize dose to the entire eye without compromising target volume coverage. In the event that the recommended maximum dose constraints provided in this section would be exceeded, the treating radiation oncologist may use their discretion to reduce target volume coverage.
- Structure definition Each eye should be separately contoured on the treatment planning CT or MR as a circular structure from the most superior to inferior aspect.

#### 5.12.3 Optic Nerves and Chiasm

- D50% < 5400cGy and D10% < 5600cGy Goal
- D50% < 5600cGy and D10% < 5800cGy Maximum
- Comment Effort should be made to avoid direct treatment of the optic nerves and chiasm without compromising target volume coverage. In the event that the recommended maximum dose constraints provided in this section would be exceeded, the treating radiation oncologist may use their discretion to reduce target volume coverage.
- Structure definition The optic nerve may be contoured on CT or MR. The contour should appear on at least two successive CT or MR images.

#### 5.12.4 Spinal Cord

- D50% < 2600cGyand D10% < 5700cGy- Goal
- D50% < 5000cGy and D10% < 5900cGy Maximum
- Comment Effort should be made to minimize dose to the spinal cord without
  compromising target volume coverage. In the event that the recommended
  maximum dose constraints provided in this section would be exceeded, the
  treating radiation oncologist may use their discretion to reduce target volume
  coverage.
- Structure Definition For the purposes of this study, the upper aspect of the spinal cord begins at the inferior border of the foramen magnum and should be contoured on the treatment planning CT. For purposes of comparison and consistency with dose volume data, the spinal cord should be contoured on a number of images to be determined by the image section thickness (CT section thickness, n=number of images; 2mm, n=30; 2.5mm, n=24; 3mm, n=20). Using these guidelines, only the superior-most 6cm of anatomic spinal cord is contoured.

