#### 5.7.2 Targeting for patients with metastatic disease

IRB Approval date: St. Jude Children's Research Hospital IRB NUMBER: Pro00004349

Craniospinal Irradiation (CSI): The CSI volume includes the entire subarachnoid volume with special attention to identification and inclusion of the cribriform plate and temporal fossae intracranially; the full width of the spinal subarachnoid space intraspinally and the inferior aspect of the thecal sac. CSI will be reserved for patients with evidence of neuraxis dissemination based on evaluation of CSF cytology or imaging of the brain and spine and will be given according to the guidelines provided below.

Primary Site Irradiation: Patients with metastatic disease may also have evidence of primary site failure and will receive supplemental irradiation to the primary site immediately following craniospinal irradiation. Targeting guidelines for the treatment of the primary site in this setting will follow the guidelines used for primary site irradiation in the absence of metastatic disease.

Metastatic Site Irradiation: Treatment of metastatic disease requires investigator discretion. All resected lesions and overt metastatic disease >0.3cm in maximal thickness should receive supplemental irradiation in addition to CSI when practical. Smaller lesions may also be treated at the discretion of the treating physician. This will include lesions in the brain and spine and using the guidelines outlined below.

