Craniospinal Irradiation-CT Planning: CT studies obtained uniquely for the CSI planning process are allowed and may also serve as the basis for planning boost treatment. CT studies will be performed whenever possible and the information used for craniocaudal intensity modulation. For the cranial component of treatment, the external contours of the skull and neck are viewed in the AP direction and points are chosen to divide the cranial field into 2-4 fields to achieve a field-within-a-field plan and lateral homogeneity over the craniocervical junction. For the spinal component of treatment, the spinal cord and canal are contoured and viewed laterally and points are chosen to divide the spinal field into 4-6 fields to achieve field-within-a-field plan and antero-posterior homogeneity over the spinal cord and thecal sac. The following parameters are suggested: volume - cranial vertex to perineum; section thickness < 5mm; image matrix - 512². The administration of IV contrast is not required.

Patients may have one or more metastatic lesions. These lesions may or may not be surgically removed. The nomenclature for the targeted volumes will follow those used for primary site irradiation with additional descriptors mean to assist in the evaluation of the case after the completion of treatment. For example, MGTV1\_intracranial or MGTV1\_right\_lateral ventricle and subsequent modifications for CTV and PTV will be helpful.

Relevant to proton therapy, the PTV may be used to select the appropriate beam size and beam arrangements to achieve lateral coverage of the targeted volume and to minimize heterogeneity. The PTV will not be used to determine the distal range for the individual proton beams but will be used to report dose according to ICRU Report-78. The proton distal target margin will be determined per beam using the guidelines noted in this protocol.

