#### 5.9.2 Prescribed dose and fractionation

IRB Approval date: St. Jude Children's Research Hospital IRB NUMBER: Pro00004349

The patient should be treated with one fraction per day. All fields should be treated each day in photon treatments. Simultaneous integrated boost is not allowed.

Table Prescribed Doses and Fractionation

Total Dose by Site	Target Volume	Dose/fraction	Number of Fractions
Neuraxis 3600-3960CcGE/cGy	CTV CSI /PTV CSI	180CcGE/cGy	20-22
Primary Site 5040-5400cGy	CTV PS /PTV PS	180CcGE/cGy	10-30
Metastases 5040-5940cGy	CTV X /PTV X	180CcGE/cGy	5-13

The total dose to the target volume CTV (proton) or PTV (photon) prescription isodose surface will be 5400CcGE/cGy administered in 30 fractions of 180CcGE/cGy. The patient should be treated with one fraction per day. All fields should be treated each day in photon treatments. Exceptions will include unanticipated changes in patient's clinical condition, logistical considerations owing to holidays, weather, equipment failure and the need to complete the course of treatment in the least number of elapsed days. Two treatments in one calendar day will be discouraged. We will consider a single fraction reduction in the dose regimen for cases where significant dose heterogeneity are encountered. Investigator discretion may be used to alter the dose per fraction 150-200CcGE/cGy per day when indicated and requires PI approval. The total dose may be attenuated - 3420CcGE/cGy instead of 3600CcGE/cGy CSI or 5040CcGE/cGy instead of 5400CcGE/cGy primary site - for patients with prior history of significant treatment-related complications or in the setting of significant dose heterogeneity or high-dose treatment volumes. We will also consider alterating the craniospinal dose when there are concerns about excessive risks regarding treatment-related complications,

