#### **5.13.2** Normal Tissue Dosimetry

The dose to the critical organs indicated should be calculated whenever they are directly included in a radiation field. A DVH must be submitted for a category of tissue called "unspecified tissue," which is defined as tissue contained within the skin, but which is not otherwise identified by containment within any other structure. A DVH for "Body" shall be submitted to enable calculation of the required volumes. "Body" is defined as the outer contour of the patient on the treatment planning CT data set.

Required DVH data regardless of primary treatment site

Required DVH
Optic Chiasm
Brainstem
Spinal Cord
Right Cochlea
Left Cochlea
Body

IRB Approval date:

Rev. 3.2 dated: 1/19/2023 Protocol document date: 1/19/2023 St. Jude Children's Research Hospital

IRB NUMBER: Pro00004349

Unspecified Tissue

Treated Volume, Irradiated Volume and Conformity Index (CI) The treated volume (TV) is the tissue volume that receives therapeutic dose. For the purpose of this protocol this would include the prescribed total dose of 54-59.4Gy and 95% of the prescribed dose. This information may be used by the investigators, along with the absolute volume of the PTV, to calculate the conformity indexes (CI) CI100% and CI95%, respectively. The irradiated volume (IV) is the tissue volume that receives a dose that is considered significant in relation to normal tissue tolerance. The descriptive statistics for these and other tissue volumes maybe used for correlation with unusual side effects or to develop practical guidelines for future brain tumor protocols.

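### When a spinal metastasis below the top 6 cm of cord is boosted, the cord limits and required cord DVH describe a different segment and can understate current-course dose by 10.8–23.4 Gy

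*Combined protocol and SAP*

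**What the plan says.** Section 5.12.4 starts the cord at the foramen magnum and fixes the number of CT slices to contour ("2mm, n=30; 2.5mm, n=24; 3mm, n=20"), so that "only the superior-most 6cm of anatomic spinal cord is contoured". Its stated reason is comparability with other dose-volume data. The same section gives the cord values: "D50% < 2600cGyand D10% < 5700cGy- Goal" and "D50% < 5000cGy and D10% < 5900cGy Maximum". Section 5.13.2 lists Spinal Cord under "Required DVH data regardless of primary treatment site" and gives no other definition of the structure.

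Patients in strata 2 and 3 (4.3) receive CSI. Section 5.7.2 asks for supplemental dose, where practical, to resected metastases and to overt ones thicker than 0.3 cm, and adds: "This will include lesions in the brain and spine and using the guidelines outlined below". The dose table in 5.9.2 reads "Metastases 5040-5940cGy" and does not separate brain from spine. Section 5.2 gives the same range after CSI of 36–39.6 Gy. Section 5.11 schedules spinal metastatic treatment alongside the primary site.

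Three other places bear on contouring. For CT-planned CSI, 5.8.3 says "the spinal cord and canal are contoured and viewed laterally", as a step in dividing the spinal field. Section 5.7 wants normal tissues outlined on every axial slice where they can be seen. Section 5.6 wants organs at risk inside the irradiated volume contoured and a DVH used to evaluate normal tissue dose.

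**The concern.** A boosted thoracic metastasis lies beside cord that is outside the structure called Spinal Cord. Followed as written, 5.12.4 and 5.13.2 then produce a cord D10% from the upper cervical segment, and the boosted cord is counted only within Body, the target volumes or unspecified tissue. Two things suffer.

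- **Plan review.** Section 5.12 asks for a quality-assurance explanation when a recommended organ dose is exceeded. An exceedance at the boosted level would not prompt one.
- **Toxicity analysis.** The Human Subjects text of the Protocol Summary lists myelopathy as a late effect. Section 2.1 names spinal cord necrosis among its greatest concerns. The hypothesis in 1.2 ties side effects to normal-tissue dose, and 1.4.2 counts planning parameters among the treatment factors. For these patients, an analysis using the required cord DVH would pair the outcome with dose from another part of the cord.

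**Working it through.** **1. The 6 cm figure.** Length = slice thickness × slice count: 2 × 30 = 60 mm, 2.5 × 24 = 60 mm, 3 × 20 = 60 mm. All three schemes in 5.12.4 give exactly 6 cm. Sections 5.6 and 5.8.3 allow CSI planning sections up to a 5 mm bound, for which 5.12.4 gives no count (60 / 5 = 12 would match).

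**2. The gap.** Inputs: CSI dose 36–39.6 Gy and metastatic-site total 50.4–59.4 Gy (5.2, 5.9.2). Assumptions: the cord beside the lesion receives the site total, and no boost reaches the top 6 cm, which therefore reads about the CSI dose. Gap = site total − CSI dose. The last two columns compare the boosted segment with the D10% values of 5.12.4.

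| CSI (Gy) | Site total (Gy) | Gap (Gy) | Below goal, 57 Gy | Below maximum, 59 Gy |
|---|---|---|---|---|
| 39.6 | 50.4 | 10.8 | yes | yes |
| 36 | 50.4 | 14.4 | yes | yes |
| 39.6 | 54 | 14.4 | yes | yes |
| 36 | 54 | 18.0 | yes | yes |
| 39.6 | 59.4 | 19.8 | no | no |
| 36 | 59.4 | 23.4 | no | no |

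In every row the 6 cm structure reads 36–39.6 Gy and passes both D10% values. The range uses the standard CSI doses; 5.9.2 also permits attenuation to 34.2 Gy, which is left out here.

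**3. Would a whole-cord D10% solve it?** Not reliably. The documents give no cord length. Assuming 25–45 cm, 6 cm is 6/45 = 13% to 6/25 = 24% of the cord. A whole-cord D10% registers a boost only if the boost covers more than 10% of the length, about 2.5–4.5 cm. A shorter boost would still be missed.

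**4. Current course against cumulative dose.** Section 2.1 discusses overlap of 54 Gy and 39.6 Gy in the cervical cord: 54 + 39.6 = 93.6 Gy. A spinal site with no earlier irradiation reaches at most 59.4 Gy. Section 5.12 says its guidelines are for the current treatment and are not cumulative.

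**5. A sign of where the cord section came from.** The D50% goal of under 26 Gy cannot be met when the segment receives 36–39.6 Gy of CSI. That suggests 5.12.4 was written with focal treatment in mind.

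**The case against.** The strongest reply is that the protocol already has the cord contoured. Sections 5.6, 5.7 and 5.8.3 point that way, 2.1 describes volumetric dose data registered to follow-up imaging, and nothing in section 11 ties an analysis to the exported 6 cm DVH. This stands to a degree: a reader might infer that the boosted cord goes unexamined or that its dose is lost, and the documents do not support that. But those sections attach no cord DVH or limit to a boosted level, and the specific definition in 5.12.4 contradicts the general wording in 5.7.

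The 6 cm rule is also deliberate. A fixed length keeps D10% and D50% comparable between patients, which is a good reason to retain it, though not to make it the only cord structure.

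Three further inferences are tempting and go too far.

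- **The protocol fails to record the cord that receives the most dose.** This can be said only of the current course. Cumulatively, the upper cervical cord, which is contoured, may receive more.
- **The limits let exceedances through generally.** They do so only near 59.4 Gy. Section 5.2 links 59.4 Gy to previously untreated brain, 5.2 makes boost dose depend on location, and 5.7.2 leaves metastatic treatment to discretion. How often spinal sites reach that level is unknown. The organ-at-risk values are also recommendations.
- **The recorded D10% always equals the CSI dose.** An infratentorial boost can raise it.

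**Conclusion.** The point holds within a defined scope: CSI patients with a boosted spinal metastasis beside cord below the top 6 cm, whose upper cord is not also boosted. For them the required cord DVH understates current-course dose to the boosted cord by 10.8–23.4 Gy, assuming the adjacent cord receives the site total. At 50.4 or 54 Gy the record is misleading but no D10% value is exceeded; at 59.4 Gy both the goal and the maximum are exceeded at that level with no flag.

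Focal-only patients and metastases within the top 6 cm are unaffected. The number affected is not given. In Table 11.0, 16 of 50 historical patients had distant and 5 had combined failure, so 21 of 50 (42%) had metastatic failure; the share with boosted spinal disease is not stated. The primary PFS and OS analyses are untouched. What is affected is plan review and the secondary dose–toxicity work.

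**What to change.** Keep the 6 cm segment as it is, for comparability. For every patient given a spinal boost:

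- export the DVH of the cord already contoured for CSI planning under 5.8.3, and add it to the required list in 5.13.2;
- report cord dose at each boosted level, for example a near-maximum dose, because a whole-cord D10% can miss a short boost;
- use the boosted-level dose where cord dose enters a toxicity analysis.

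The sponsor should state which structure the 5.12.4 values govern and reconcile 5.6–5.7, 5.9.2, 5.12.4 and 5.13.2, including the slice count for thicker CSI sections and the D50% goal under CSI. No dose or limit is proposed here.

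The cost is small: one more DVH and one dose value per boosted level, from contours that 5.8.3 already calls for in CT-planned CSI. Plans already treated can be re-queried where the planning data are stored.
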